Study Procedure Description	Benefits	Compensation & Costs
Subject Population	Risks	

GENERAL STUDY INFORMATION

Study Title

Include the study title below.

FUEL: Food, fUn, frEsh, famiLy program. Promoting children's diet through afterschool program and family support.

1 Review Type (Choose one)

Please choose which level of review best fits your research. This is an investigator's assessment of review and does not preclude the IRB from alternate determinations. In cases where the investigator and the IRB's determination of review conflict, the IRB's determination will be considered the official determination.

Note: Expedited review does not refer to the timeliness of the review of your protocol, but specific categories of research defined by OHRP. If you would like help determining which type of review best fits your research study, please contact the IRB staff in the Office of Research Support & Compliance:

<https://research.utexas.edu/ors/human-subjects/get-help/>

a **Full Board Review – Greater than Minimal Risk Research**

b **Expedited Review – Minimal Risk Research**

2 Research Hypotheses

Please describe the research aims and hypotheses in the box below. To input text, click in the box below and start typing.

Note: Procedures will be explained in a separate section below.

Our primary hypothesis is that the effect of an after-school curriculum on nutrition and physical activity for elementary aged children improves overall child diet better when resources to encourage healthier eating are provided to caregivers at the same time than if they are not provided.

3 Study Background

Provide the rationale and the scientific or scholarly background for the proposed activity, based on existing literature (or clinical knowledge). Describe the gaps in current knowledge that the project is intended to address.

One approach to improving child health trajectories including diet has focused on after-school programming. A prominent example, the “Coordinated Approach to Child Health” (CATCH) program, provides curriculum on nutrition and physical activity. CATCH has, over almost two decades of implementation and assessment, shown positive impacts on reducing the incidence of obesity and improving child diet (Hoelscher et al, 2010). It is regularly used by organizations such as the Boys and

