Provide a brief description of the study design or data collection methodologies. Details regarding protocol specific research procedures will be discussed in a later section.

Design: A two-arm randomized trial.

Randomization:

- Eligible households with at least one child (reference child) in the BGCAA after-school program whose caregiver/parent (guardian) (reference caregiver) consents to participate in the study will be randomized to either the active intervention or the control (1:1 ratio). Randomization will be stratified by the family's SNAP beneficiary status as SNAP could affect uptake of treatment elements offered in the family support arm.

Blinding: Outcome assessors, principal investigator, and biostatistician are blinded to participant allocation. Participant and other staff are unblinded.

Study arms (19 weeks) (Figure 1):

Randomized arms

Children in both intervention and control arms participate in the BGCAA's after-school program with CATCH curriculum.

1. Across participating school sites, the whole BGCAA's after-school program runs for 3h, Mon-Fri for the school year. Children enrolled are expected to attend a minimum of 2x/week.
2. CATCH curriculum will be delivered as a component of the after-school program in blocks of 45-60 min, twice a week.
3. Children also participate in active recreational time (approx. 60 min, offered 1x/week at a minimum) which consists of a mixture of free play, structured physical activity games, and/or sports activities (including soccer, football, and basketball).

Intervention arm: BGCAA after-school program + Family support

1. Children participate in the BGCAA's after-school program with CATCH curriculum as described above.
2. The child's caregiver will receive the following:
 - Family tip sheets sent via mobile text at the start of the program and then every 3 weeks, to a total of 6 txt messages.
 - Weeks 1-4 (4 weeks):
 - i. Welcome package mailed to the family's residence approximately in the first week of the program.

- ii. Weekly: 1 box of produce
- iii. Recipes accompanying each box (sample recipe card attached to submission)
- iv. Bi-Weekly: Grocery store gift cards (2x \$20, to a total of \$40)
- Weeks 5-19 (total of 10 weeks over the 19-week study timeline):

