Because both the primary and secondary outcome measures are continuous, normally distributed measures, we anticipate having to rely on normal theory analytic methods. Specifically, mixed linear regressions on the primary (HEI) and secondary outcome measures (such as Fruits & Vegetable subscores, BMI and parent HEI) will be fitted to test differential trajectories for two groups from baseline to midpoint and end point assessment of the program, time expressed as days elapsed from baseline. These models readily accommodate differential dropout in the arms with maximum likelihood estimation, random intercepts, and also adjust for any clustering effect of the BGCAA sites. Because randomization will be stratified by whether the family are SNAP recipients or not, the main effect of family's SNAP beneficiary status will be included in all models in addition to the main target terms of interest: two-way interactions of time X treatment, time X SNAP, and their three-way interaction. Overall alpha will be set at 0.05 for each child outcome on these target terms.

In addition to these intention-to-treat (ITT) analyses we will also conduct as-treated (AT) analyses incorporating the 'dose' variable that will be formed based on implementation database elements that permits the tracking of program elements consumed/ picked up/ attended by the target child and his/her parent/guardian in the two active arms. In AT models, total dose taken-up by the end of the program will enter into product terms with time. As is typical, we expect the AT models to have greater sensitivity/ precision in estimating the added value of the family support beyond the elements of the after-school program with CATCH for change in HEI and secondary outcomes. In addition the dose variable sheds light on the effects of Boys and Girls Club programming, including CATCH, regardless of other incentives. Statistical controls for family demographic characteristics, food insecurity, child age, sex, and SNAP beneficiary status will be included in the AT framework as 'dose' is not completely controlled by the randomization and hence would be expected to be correlated with these characteristics (e.g. economically disadvantaged families may be more likely to uptake more of the program elements).

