We will invite all families across all 11 participating sites. Given numbers from the current year, we expect total number that could be invited (meeting inclusion/ exclusion criteria) to be 350 total index parent and child pairings. Below we discuss various realistic recruitment and retention scenarios given the capacity of our partner, BGCAA. Our aim will be to maximize recruitment but are prepared for various recruitment scenarios.

15 Sample size rationale

Describe your sample size rational below.

We are conducting both as-treated (AT) and intention-to-treat (ITT) analyses.

To inform our sample size calculations and power for the ITT and AT analyses, we relied on information from the pilot trial conducted at BGCAA sites in the spring of 2021. The pilot also used the SPAN tool to measure diet for child and caregiver (Kahlon et al., 2022).

For the AT analysis, we use the results of the pilot from Spring of 2021 showing a dose response correlation, which was $r = 0.31$. We have 80% power to detect this association with total $N = 79$. Even if the enrollment and retention is as low as $n = 64$ for each active arm, we would be able to detect a dose-response correlation as low as 0.24 in the AT framework.

From the 2021 study, the effect size for the overall child's HEI (Healthy Eating Index) at the end of the study was .47 with an ICC of .20 for person x site clusters. For the present study, to be able to detect an identical difference between the two randomized arms (Program+Family Support and After-school program only) with 80% power at $\alpha = .05$, we would need to retain 120 children in each arm. Considering a 15% attrition rate, a target recruitment of approx. 140 children into each active arm would permit sufficient power to observe the targeted moderate group difference.

Given the recruitment pool for our sample is limited by the BGCAA program capacity, we estimated the changes in effect sizes (i.e., our ability to detect differences) in two scenarios, maintaining 80% power at $\alpha = .05$.

Assuming that all eligible households will be invited to participate and that a conservative potential pool of approx. **300 households** will be maintained in the fall (in the current school semester, Boys and Girls Club has approximately 313 households attending their after-school program with at least one child), we can expect the following:

- If we successfully enroll 75% in the study, N=226

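### The only ITT model described contains time x treatment x SNAP but no stated SNAP coding or SNAP-averaged contrast, so with a 0/1 indicator its time x treatment term is the arm difference in one SNAP stratum, not the overall difference that was powered

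*Combined protocol and SAP*

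**What the plan says.** Section 5 fits mixed linear models to "test differential trajectories for two groups from baseline to midpoint and end point assessment of the program", with "time expressed as days elapsed from baseline". It adds that "the main effect of family's SNAP beneficiary status will be included in all models", and lists as the terms to be tested the "two-way interactions of time X treatment, time X SNAP, and their three-way interaction". On error control it says: "Overall alpha will be set at 0.05 for each child outcome on these target terms". It describes no second ITT model without the three-way term. It does not say how SNAP is coded, whether a contrast averaged over SNAP will be formed, or which term answers the primary hypothesis.

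Section 2 asks whether the after-school curriculum "improves overall child diet better when resources to encourage healthier eating are provided to caregivers" at the same time. That is one question about all families. Section 15 sets the sample size "to be able to detect an identical difference between the two randomized arms", with no SNAP subgroup or interaction in the calculation. Section 4 (Randomization) gives the reason for stratifying: "SNAP could affect uptake of treatment elements offered in the family support arm".

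**The concern.** Once a model holds a three-way interaction, the meaning of each two-way term inside it depends on how the third variable is coded. A reader of the results would naturally take the time x treatment line as the primary answer. Under the commonest coding of a yes/no variable, 0/1, that line describes only the families coded 0, and it would change if the labels were swapped.

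Two things are at stake. The first is the estimand: if family support works differently in SNAP and non-SNAP households, the reported term differs from the effect in the hypothesis. The second is precision: a term estimated from one stratum has a larger standard error than the overall contrast, so the planned power does not carry over to it. An analyst who notices this later would have to choose a coding or contrast after the plan was fixed, and that choice moves both the estimate and the p-value.

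**Working it through.** **Inputs.** From the plan: 1:1 allocation stratified by SNAP (section 4); the model terms, time in days, and alpha 0.05 (section 5); 80% power, d = 0.47, ICC 0.20 and 120 retained per arm (section 15). Assumed, because not given: a two-sided test; a share p of families in the SNAP stratum coded 0, taken as 30%, 50% or 70%; visits at days 0, 49 and 140; a random intercept with within-child correlation 0.3 or 0.5; no site effect.

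**The plan's own figure.** Without clustering, d = 0.47 needs about 2 x 7.85/0.47² = 71, or 72 per arm with the t-test. The stated 120 is 120/72 = 1.67 times that. At ICC 0.20 this corresponds to a cluster size of 1 + 0.67/0.20, about 4.3, but no cluster size is given. So 120 cannot be reproduced, nor can it be called wrong. The check below takes the stated 80% as its starting point and does not otherwise depend on 120.

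**What the coefficient means.** Let A be arm, S be SNAP and t be time. The arm difference in slope is b(tA) + b(tAS) x S.
- S coded 0/1: b(tA) is the slope difference where S = 0. The overall effect is b(tA) + (1 - p) x b(tAS).
- S coded +/-0.5: b(tA) is the unweighted mean of the two stratum effects.
- S centred at its sample proportion: b(tA) is the mean weighted by stratum share, that is, the overall effect.

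This holds whether or not treatment x SNAP, which section 5 does not list, is also in the model. In a large simulated data set with stratum effects 0.20 and 0.74, the 0/1 term came out at 0.19-0.20 with an equal split (overall effect 0.47) and at 0.20-0.21 with 30% in the reference stratum (overall effect 0.3 x 0.20 + 0.7 x 0.74 = 0.578). Centring SNAP, or omitting the three-way term, gave 0.463 and 0.585.

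**Precision of the 0/1 term.** R is the variance of the time x treatment term divided by its variance without the three-way term. With all lower-order terms, R = 1/p. With the listed terms plus time and treatment, R comes from the generalised least squares information matrix. Power = Φ(2.80/√R - 1.96), with equal effects in both strata.

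| Reference share p | R, all lower-order terms | Power | R, listed terms | Power |
|---|---|---|---|---|
| 30% | 3.33 | 34% | 2.54-2.80 | 39-42% |
| 50% | 2.00 | 51% | 1.66-1.77 | 56-59% |
| 70% | 1.43 | 65% | 1.28-1.33 | 68-70% |

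At p = 50% with all lower-order terms, restoring 80% power would take 120/0.5 = 240 retained per arm.

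**Other readings.**
- Centred SNAP: R = 1.00, power 80%.
- +/-0.5 coding: R = 1/(4p(1 - p)), which is 1.00 at 50% and 1/0.84 = 1.19 at 30% or 70%. Power is 80% and about 73%.
- Joint 2-df test of time x treatment and the three-way term: noncentrality 2.80², about 7.85, against a critical value of 5.99. Power is about 71%.

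**The case against.** A reader might infer that the plan tests the wrong parameter and that the trial's result will rest on one stratum. The documents do not support that. Section 5 states no coding, and the same model with centred SNAP delivers the overall effect at no loss. With +/-0.5 coding the loss is small. Nor does section 5 say that the time x treatment coefficient alone decides the trial. A joint test of the two treatment terms is also a possible reading; it would use both strata and would not depend on coding. All of this stands, and it makes the defect conditional on 0/1 coding.

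A reader might also infer that SNAP is known to change the effect. Section 4 says only that it could affect uptake, and no section gives a difference in diet effect by SNAP status. The stratum effects used above are illustrations.

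The 80% starting point is itself loose. Section 15 powers an end-of-study standardised difference, while section 5 tests a slope in days. The four recruitment scenarios in section 15 are about 1.2 times the unclustered detectable effect; the same rule at 120 per arm gives 0.363 x 1.2 = 0.436. On that anchor the 50% figure with all lower-order terms would be Φ(2.80 x (0.47/0.436) x √0.5 - 1.96), about 57% and not 51%.

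What the objection does not remove is the gap itself. None of the harmless choices is written down. A joint test of the treatment terms would not be the single contrast that was powered, and a joint test of all three target terms would include time x SNAP, which is not a treatment effect.

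**Conclusion.** The point holds in conditional form. The only ITT model described makes the three-way term a target and leaves open which quantity answers the primary hypothesis. Fitted as listed with a 0/1 indicator, it gives a stratum-specific and less precise time x treatment estimate: about 34-42%, 51-59% or 65-70% power for a reference share of 30%, 50% or 70%, against 80% for the overall contrast. Under the other readings power lies between about 71% and 80%.

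The algebra is certain. The power figures are illustrative: they rest on an assumed SNAP share, equal effects in both strata, a two-sided test, and the stated 80% applying to the overall contrast. The listed-terms ranges also depend on the assumed visit days and correlations. The documents do not show that 0/1 coding will be used or that the effects differ by SNAP.

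**What to change.** In section 5, name the primary ITT test as the arm difference in trajectory averaged over SNAP by stratum share. Either of two forms will do:
- a primary model with time, treatment, SNAP, time x treatment, time x SNAP and site, in which time x treatment is the SNAP-adjusted overall difference; or
- the three-way model with SNAP centred at its sample proportion, reading time x treatment from it.

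State that time x treatment x SNAP is a secondary test of effect modification, so the moderator question is kept. This is a change of a sentence or two, with no new data and no change to conduct. Naming one contrast also largely settles how the 0.05 is shared among the target terms, so the two matters can be handled in the same edit.

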 - i. For five weeks, an optional online form (or “*goal sheet*”) will be sent to the parent/caregiver (5 sheets in total) with questions about trying new FV items to be completed within the next 7 days. As an incentive, a \$10 gift card will be sent the following week to those who complete it (a potential total of \$50).
 - ii. Week 11: \$20 Grocery store gift card. Based on disruptions due to the school year breaks, we will provide an extra \$20 gift card to re-engage the week after a school holiday.

Control arm: BGC after-school program only

1. Children participate in the BGCAs after-school program with CATCH curriculum as described above.
2. At the end of the study, they will receive \$120 as grocery store gift cards.

[figure not shown]

Figure 1. Study design: 2 randomized arms

Outcomes:

- Primary:
 - Child's diet quality: measured by Healthy Eating Index, HEI, scores calculated from the Texas School Physical Activity and Nutrition (SPAN), 2nd Grade.
 - Child's fruits and vegetable consumption, measured by SPAN, 2nd Grade.
- Secondary outcomes:
 - Caregiver/parent diet quality, measured by HEI scores calculated from the SPAN, 8th Grade.
 - Child's physical activity levels
 - Child's body mass index, as percentile of BMI-for-age

Study measurements:

Timepoint measurements for all study participants (child-parent dyads) include:

- baseline (approximately up to 4 weeks prior to the first produce bag and grocery store gift card being distributed). Height and weight will be taken during the first 1-2 weeks of the research program start date during a BGCAA field day.
- mid-point (planned for approximately weeks 5-8)
- end-point (approximately between weeks 16 and 21). Height and weight will be taken during the 19th week of the program at the BGCAA's field day.

Outcomes	Tool	Time points	Administration
Child's Diet (primary)	TX SPAN 2 nd grade 2019-2020 – Dietary questions	Baseline, Mid-point, End point	Child, Guardian-reported Structured interview over the phone by RA
	SPAN Healthy Eating Index scores (includes total, healthy, and unhealthy scores)	Baseline, Mid-point, End point	Child, calculated from SPAN
Physical Activity	TX SPAN 2 nd grade 2019-2020 – Physical activity questions	Baseline, End point	Child, guardian-reported Structured interview over the phone by RA
	Physical Activity Questionnaire – Children		

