 - i. One welcome package will be mailed to the family's address at the start of the program containing: A welcome letter, a calendar of important dates related to the program and some educational handouts such as healthy food choices with "Go, Slow, Whoa List", tip sheets for activities, food allergy information, and child-friendly recipes. Examples attached to this submission. Participant's address will be obtained via the demographic questionnaire at baseline.
 - ii. Weekly: 1 box of produce to be delivered centrally to each of the participating after-school sites and will be distributed by BGCAA to the participating parents/caregivers during child pickup. At the BGCAA housing sites, some children may walk home with the produce bag and a BGCAA staff member will assist if needed (which is normal protocol for BGCAA). Participants cannot pick the groceries that are provided, and therefore will not have control over potential allergens in the box. As such, participants with known food allergens related to produce items will be excluded from the study.
 - iii. Recipes accompanying each box (sample recipe card attached to submission). Recipes will be the same for all participants and will be sent via a text message link. The program team will also provide physical copies of the recipes in the event they cannot access the text link. Bi-Weekly: HEB Grocery store gift cards (total of \$40)
 - **Weeks 5-16** (total of 10 weeks over the 19-week study timeline):
 - i. At the start of weeks 5, 7, 9, 12, and 14: An optional online form (or "*goal sheet*") will be sent to the parent/caregiver (5 sheets in total) with questions about the produce items (including but not limited to: bananas, carrots, zucchini, squash, etc.) they received to be completed within the next 7 days. As an incentive, a \$10 HEB gift card will be sent the following week to those who complete it (a potential total of \$50).
 - ii. Week 11: \$20 HEB Grocery store gift card

Since the goal sheet will contain identifiers (such as names), this form will be built in a HIPAA compliant database, such as REDCap, Qualtrics, or other secure database where the information collected will be securely stored and then checked by unblinded Factor health staff for appropriate incentive distribution.

Arm #2 – Control arm: BGCAA after-school program only

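### The as-treated dose × time coefficient is a confounded association with a mixed dose, not the added value of family support, and the precision expected of it is unsupported

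*Combined protocol and SAP*

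**What the plan says.** Section 5 adds as-treated (AT) models to the intention-to-treat (ITT) models. The ITT models are mixed regressions over baseline, mid-point and end-point, with "time expressed as days elapsed from baseline". In the AT models "total dose taken-up by the end of the program will enter into product terms with time".

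Dose is built from "program elements consumed/ picked up/ attended by the target child and his/her parent/guardian in the two active arms". The section says that "we expect the AT models to have greater sensitivity/ precision in estimating the added value of the family support", over and above what the club provides to both arms, and that the same variable also informs on the club programming and CATCH.

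The section concedes that randomisation does not fully control dose. It adjusts for family demographics, food insecurity, child age, sex and SNAP status. Its exploratory paragraph then says that family-support elements call for more motivation from the parent, and plans to relate separate aspects of dose to response.

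On timing, section 4 has "mid-point (planned for approximately weeks 5-8". Section 11 sends goal sheets "At the start of weeks 5, 7, 9, 12, and 14" and a further gift card in week 11. Section 15 gives the AT analysis its own power case: a pilot correlation of 0.31 with a total N of 79.

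**The concern.** Three features combine.

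- **Mixed exposure.** A single total cannot separate attendance, which both arms have, from support uptake, which only one arm has. The plan gives no dose formula and does not say whether arm stays in the AT model.
- **Self-selection.** Motivation is named as a driver of uptake but is not a covariate. The unblinded caregiver completes the goal sheets and usually reports the child's diet, so motivation can affect both dose and reported outcome.
- **Order in time.** Part of the total accrues after the mid-point measurement that it helps to explain.

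What is at stake is interpretation. A difference between more and less engaged families could be reported as a dose response and credited to family support, with the plan's own text describing that analysis as the more sensitive one.

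**Working it through.** **1. The plan's AT figure.** Inputs from section 15: r = 0.31, 80% power, alpha .05 (taken as two-sided, since one-sided gives N = 64 and does not fit). Fisher z: N = ((1.960 + 0.842)/atanh(r))² + 3. For r = 0.31 this is 79.4, against the stated 79; power at N = 79 is 79.8%. With 64 per arm (N = 128) the smallest detectable correlation is tanh(2.802/√125) = 0.245, against the stated 0.24. Both figures reproduce, but only as a plain bivariate correlation with no clustering and no covariates.

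**2. Comparison with the ITT figure.** Section 15 asks for 120 per arm for d = 0.47 with an ICC of .20. Without clustering, n = 2 × 2.802²/0.47² = 71.1, so 72 per arm. The plan's 120 therefore carries an inflation of about 120/71.1 = 1.7. On the correlation scale d = 0.47 is 0.47/√(0.47² + 4) = 0.23. So N = 79 and N = 240 differ in the target quantity, the effect assumed (0.31 against 0.23) and the clustering allowance. They do not show that AT is more precise for the same effect.

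**3. What a total-dose coefficient estimates.** Write D = C + S, with C attendance and S family-support uptake (S = 0 in controls), and let their true slopes be b_C and b_S. Without confounding or other covariates, the coefficient on D is

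[b_C Cov(C, D) + b_S Cov(S, D)] / Var(D).

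If b_S = 0 and b_C > 0, it is still positive whenever Cov(C, D) > 0. A non-zero coefficient is therefore compatible with no added value of family support, even before self-selection enters.

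**4. Self-selection.** The documents give no confounding strength, so a residual correlation r after adjustment is assumed, with no causal effect of dose. Rejection probability = Φ(atanh(r)√(N−3) − 1.96) + Φ(−atanh(r)√(N−3) − 1.96). The sample sizes are section 15's retained 64 and 96 per arm.

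| Assumed r | N = 128 | N = 192 |
|---|---|---|
| .05 | 9% | 11% |
| .10 | 20% | 28% |
| .15 | 39% | 55% |

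**5. Simulation closer to the planned model.** There were 2,000 trials per scenario, three waves, random intercepts, no effect of family support, and dose made up of family-support elements only. Site clustering and covariates were left out. Rejection rates at nominal 5%:

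| Scenario | Dose × time, N = 128 | Dose × time, N = 240 |
|---|---|---|
| No confounding, no reverse timing | 6% | 6% |
| Motivation shifts outcome by 0.2 / 0.3 / 0.5 SD per SD | 11 / 16 / 35% | 14 / 24 / 57% |
| Late uptake follows mid-point change, log-odds 0.3 / 0.5 per SD | 5 / 7% | 6 / 8% |

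ITT time × treatment stayed at about 5–7% throughout. With arm also in the dose model, the motivation rows become 27 / 47 / 85% and 41 / 73 / 99%, and the timing rows 11 / 21% and 16 / 33%.

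**6. Timing.** Gift-card value in the intervention arm is 40 + 5 × 10 + 20 = 110 dollars. Even with the mid-point at week 8, the sheets of weeks 9, 12 and 14 and the week-11 card come later: 3 × 10 + 20 = 50 dollars, or 45%. So do 11 of the 19 program weeks (58%).

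**The case against.** The strongest reply is that AT is a declared supplement to ITT, the plan admits that dose is not randomised, it adjusts for baseline characteristics, and its exploratory paragraph already separates aspects of dose and sets a multiplicity rule. All of that is true, and it limits the point. It does not remove it. The separation is not applied to the AT model, AT is not labelled exploratory, and it has its own power case and precision statement.

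Several stronger readings are tempting but go beyond the documents.

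- **AT could rescue a null ITT result.** No rule lets AT replace ITT, and the alpha statement is attached to the ITT terms.
- **The plan asserts that AT estimates the randomised contrast better.** It states an expectation about the added value of family support and does not mention a randomised contrast.
- **Timing is the main fault.** Produce boxes and the first 40 dollars of cards come in weeks 1–4, and total dose precedes most end-point measurement. Reverse timing alone gave 5–8%; higher rates needed arm in the model, which the plan does not specify.
- **Leavers bias the slope through low dose.** Section 35 says only that they may be removed. Bias would also require leaving to be related to diet change.
- **Bias must favour the intervention.** Section 5's own example, that disadvantaged families may take up more, could pull towards the null.
- **No dose model could ever work.** With separately defined doses and no unmeasured confounding, one could estimate a dose response. The plan provides for neither.

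**Conclusion.** The point holds as one of interpretation and specification. As written, the AT coefficient is an association with a mixed, self-selected total, and it does not estimate the added value of family support. The expected gain in sensitivity or precision has no support in the plan, and the N of 79 does not supply it. The randomised ITT comparison is undamaged.

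The size is uncertain. The 9% to 39% at N = 128 rests on an assumed residual correlation of .05 to .15 and a bivariate test; smaller confounding gives less. The simulated rates likewise show direction and range, not a forecast. Self-selection and the mixed dose are the main issues, and post-mid-point dose is secondary. The change is worth making before analysis but does not threaten the trial.

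**What to change.** 1. In the AT model, carry over the separate aspects of dose from the exploratory paragraph. Define attendance/CATCH dose and family-support dose, give the formula for each, and enter them as distinct terms. State whether arm is in the model.
2. Where uptake records are dated, use dose accrued up to each visit. Otherwise relate total dose only to end-point change.
3. Label the AT model exploratory and associational, and name motivation as an unmeasured confounder.
4. Delete the sentence expecting greater sensitivity or precision for the added value of family support.

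Optionally, add a complier-average estimate with randomised arm as the instrument, as a sensitivity analysis. It has a wider interval and, with no support dose in controls, essentially rescales the ITT estimate. It also assumes that arm acts only through measured dose, which fails unless tip sheets, the welcome package and recipes are counted as dose.

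**Cost:** SAP wording and modest programming. Section 5 says elements are tracked but not that they are dated, so the feasibility of visit-specific dose must be confirmed.
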